4.4. Randomization

Patients will be randomized 1:1 to either bardoxolone methyl or placebo. Randomization will be performed using an interactive web response system (IWRS) and will be stratified by eligibility eGFR category (30 to <60; ≥60 to 90 mL/min/1.73 m²), concomitant tolvaptan use (yes, no), and screening ACR (≤300 mg/g, >300 mg/g). Eligibility eGFR is the average of the screening eGFR visits. Patients randomized to placebo will remain on placebo throughout the study, undergoing sham titration.

4.5. Clinical Assessments

All patients in the study follow the same visit and assessment schedule for the duration of the trial. [Table 2](#) lists the overall schedule of assessments for the study.

Table 2. SCHEDULE OF ASSESSMENTS

	Screening Period		Treatment Period											
	Screen A ^a	Screen B ^b	Day 1 ^c	Wk 1 (Phone)	Wk 1	Wk 2 (Phone)	Wk 2	Wk 3 (Phone)	Wk 4	Wk 4 (Phone)	Wk 5 (Phone)	Wk 6	Wk 7 (Phone)	Week 8
	Up to Day -90	Up to Day -30	Day 1	Day 3 ±2 Days	Day 7 ±3 Days	Day 10 ±2 Days	Day 14 ±3 Days	Day 21 ±2 Days	Day 28 ±3 Days	Day 31 ±2 Days	Day 38 ±2 Days	Day 42 ±3 Days	Day 45 ±2 Days	Day 56 ±3 Days
Informed Consent/Assent	X													
Inclusion/Exclusion	X		X ^d											
Demographics & Baseline Disease Characteristics	X													
Prior and Concomitant Medications	X	X	X	X	X	X	X	X	X	X	X	X	X	X
Medical History	X													
Height ^e	X	X	X		X		X		X			X		X
Weight in Clinic	X		X		X		X		X			X		X
Weight at Home			-----X-----											
Dispense Weight & Study Drug Diary			X				X		X			X		X
Collect/Review Weight & Study Drug Diary				X	X	X	X	X	X	X	X	X	X	X
ECG	X													
Echocardiogram ^f	X													
Vital Sign Measurements	X	X ^e	X		X		X		X			X		X
Comprehensive Physical Exam	X		X											
Targeted Physical Exam					X		X		X			X		X
Pregnancy Test for WOCBP ^h	X	X	X						X					X
Study Drug Administration			-----X-----											
Dispense Study Drug			X				X		X			X		X
Collect Study Drug							X		X			X		X
Telephone Contact				X		X		X		X	X		X	
Adverse Event Collection			X ⁱ	X	X	X	X	X	X	X	X	X	X	X
Kidney Ultrasound ^j	X													
Clinical Chemistry (incl. eGFR) ^k	X	X	X		X		X		X			X		X
BNP and NT-proBNP	X		X		X		X		X			X		X
Hemoglobin A1c	X													
Hematology	X		X				X		X			X		X
Coagulation			X				X		X			X		X
Basic Lipid Panel			X											
Urinalysis and Microscopy	X		X				X		X			X		X
Urine Collection for ACR ^l		X							X					X
Virus Serology	X													
PK Samples ^m														
SARS-CoV-2 Antibody Test			X											
Ambulatory Blood Pressure Monitoring ⁿ	X ^p													
Tanner Staging ^q			X											

	Treatment Period								
	Wk 12	Wk 24	Wk 36	Wk 48	Wk 52 (B)	Wk 64	Wk 76	Wk 88	Wk 100 or End of Treatment
	Day 84 ±3 Days	Day 168 ±3 Days	Day 252 ±3 Days	Day 336 ±3 Days	Day 364 ±3 Days	Day 448 ±5 Days	Day 532 ±5 Days	Day 616 ±5 Days	Day 700 -5 Days (+0 Days)
Informed Consent/Assent									
Inclusion/Exclusion									
Demographics & Baseline Disease Characteristics									
Prior and Concomitant Medications	X	X	X	X	X	X	X	X	X
Medical History									
Height ^e	X	X	X	X	X	X	X	X	X
Weight in Clinic	X	X	X	X	X	X	X	X	X
Weight at Home	-----X-----								
Dispense Weight & Study Drug Diary	X	X	X	X	X	X	X	X	
Collect/Review Weight & Study Drug Diary	X	X	X	X	X	X	X	X	X
ECG				X	X				X
Echocardiogram ^f									
Vital Sign Measurements	X	X	X	X	X	X	X	X	X
Comprehensive Physical Exam					X				X
Targeted Physical Exam	X	X	X	X		X	X	X	
Pregnancy Test for WOCBP ^h	X	X	X	X	X	X	X	X	X
Study Drug Administration	-----X-----								
Dispense Study Drug	X	X	X	X	X	X	X	X	
Collect Study Drug	X	X	X	X	X	X	X	X	X
Telephone Contact									
Adverse Event Collection	X	X	X	X	X	X	X	X	X
Kidney Ultrasound ⁱ									
Clinical Chemistry (incl. eGFR) ^k	X	X	X	X	X	X	X	X	X
BNP and NT-proBNP	X	X	X	X	X	X	X	X	X
Hemoglobin A1c	X			X					X
Hematology	X	X	X	X	X	X	X	X	X
Coagulation	X	X	X	X	X	X	X	X	X
Basic Lipid Panel					X				X
Urinalysis and Microscopy	X	X	X	X	X	X	X	X	X
Urine Collection for ACR ^l	X	X	X	X	X	X	X	X	X
Virus Serology									
PK Samples ^m	X								X
SARS-CoV-2 Antibody Test					X				
Ambulatory Blood Pressure Monitoring ^o	X			X				X ^r	
Tanner Staging ^q					X				

	Off-Treatment Period ³						
	Wk 103	Wk 104 (A)	Wk 104 (B)	Wk 108 (A)	Wk 108 (B)	Wk 112 (A)	Wk 112 (B)
Off-Treatment: Patients who continued study drug through Wk 100 (visits based on date of last dose)	Day 21 – 25 after last dose	Day 28 – 35 after last dose	Day 29 – 36 after last dose	Day 56 – 63 after last dose	Day 57 – 64 after last dose	Day 84 – 91 after last dose	Day 85 – 92 after last dose
Follow-Up: Patients who discontinued study drug prior to Wk 100 (visits based on Day 1 date)	Day 721 – 725	Day 728 – 735	Day 729 – 736	Day 756 – 763	Day 757 – 764	Day 784 – 791	Day 785 – 792
Informed Consent/Assent							
Inclusion/Exclusion							
Demographics & Baseline Disease Characteristics							
Prior and Concomitant Medications	X	X	X				
Medical History							
Height ^e	X	X	X	X	X	X	X
Weight in Clinic			X		X		
Weight at Home							
Dispense Weight & Study Drug Diary							
Collect/Review Weight & Study Drug Diary							
ECG			X		X		
Echocardiogram ^f							
Vital Sign Measurements			X		X		
Comprehensive Physical Exam			X		X		
Targeted Physical Exam							
Pregnancy Test for WOCBP ^h			X		X		
Study Drug Administration							
Dispense Study Drug							
Collect Study Drug							
Telephone Contact							
Adverse Event Collection	X	X	X	X	X	X	X
Kidney Ultrasound ⁱ							
Clinical Chemistry (incl. eGFR) ^k	X	X	X	X	X	X	X
BNP and NT-proBNP			X		X		
Hemoglobin A1c							
Hematology			X		X		
Coagulation			X		X		
Basic Lipid Panel			X		X		
Urinalysis and Microscopy			X		X		
Urine Collection for ACR ^l			X		X		
Virus Serology							
PK Samples ^m	X		X		X		
SARS-CoV-2 Antibody Test					X		
Ambulatory Blood Pressure Monitoring ^o							
Tanner Staging ^q					X		

Abbreviations: ABPM = ambulatory blood pressure monitoring, ACR = albumin to creatinine ratio, ADPKD = autosomal dominant polycystic kidney disease, AE = adverse event, BNP = B-type natriuretic peptide, ██████████, ECG = electrocardiogram, eGFR = estimated glomerular filtration rate, IRB/EC = institutional review board/ethics committee, IWRS = Interactive Web Response System, NT-proBNP = N-terminal pro-brain natriuretic peptide, ██████████

██████████, PK = pharmacokinetic, SARS-CoV-2 = Severe Acute Respiratory Syndrome Coronavirus 2, Wk = week, WOCBP = women of child-bearing potential

-
- ^a Total Screening period should not exceed 90 days.
- ^b Screen B visit should be at least 1 day after Screen A and no more than 30 days prior to Day 1.
- ^c Day 1 should be the day of randomization and administration of the first dose. Where randomization in the IWRS must occur earlier than Day 1, the Day 1 visit must align with the administration of the first dose. **On Day 1, all procedures must be performed before study drug administration.**
- ^d Screening eligibility procedures do not need to be repeated on Day 1; however, a review of any changes in eligibility criteria should be evaluated prior to Day 1 procedures
- ^e Height will be recorded in centimeters. Adult patients (18≤age≤70 years at Screen A visit) will be measured at Screen A only. Adolescent patients (12≤age<18 years at Screen A visit) will be measured at all specified timepoints.
- ^f An echocardiogram performed during screening or within 6 months prior to Day 1 may be used to determine eligibility.
- ^g Screen B vital sign measurements are needed only if re-assessing blood pressure for eligibility.
- ^h A serum pregnancy test will be performed at the Screen A visit for WOCBP or at any point in time if a pregnancy is suspected. All other pregnancy assessments will be urine pregnancy tests. Additional pregnancy assessments will be performed more frequently if required by local law or requested by local regulatory authorities or IRBs/ECs.
- ⁱ AE assessments on Day 1 should be performed following study drug administration.
- ^j Kidney ultrasound (historical or one obtained during screening) may be used to diagnose ADPKD for patients without a prior ADPKD diagnosis.
- ^k eGFR will be calculated and appear on lab reports for Screen A and Screen B visits, eGFR will no longer be calculated for any visits after the Screening period.
- ^l Albumin to creatinine ratio will be measured by first morning void spot urine collection. Appropriate containers for the collection will be provided to the patient at the visit prior to collection.
- ██████████
- ██████████
- ⁿ Patients must refrain from taking study drug prior to coming to the clinic for PK draws at Week 12 and Week 100.
- ^o Ambulatory Blood Pressure Monitoring (ABPM) is an optional sub-study for adult patients (18≤age≤70 years at Screen A) who enroll under protocol version 6.0 (or greater) and consent to the procedure prior to randomization. See Protocol Section 9.10.33 for details and timing on ABPM. ABPM will not be performed on adolescent patients (12≤age<18 years at randomization).
- ^p For patients who consent to the optional ABPM sub-study, the initial (baseline) 24-hour monitoring assessment must be done during the Screening period prior to Day 1. See Protocol Section 9.10.33 for detailed information.
- ^q Adolescent patients (12≤age<18 years at Screen A visit) will be assessed by Tanner staging at all specified timepoints.
- ^r For adult patients who consent to the optional ABPM sub-study, the final 24-hour monitoring assessment occurs after Week 88 and prior to Week 100 (last dose). For patients who discontinue study drug prior to Week 100, patients who consented to ABPM should have the assessment at End of Treatment if no ABPM was conducted in the four weeks prior to the date of last dose.
- ^s See Protocol Section 8.3.3 and Protocol Section 8.5.1 for details on the Off-Treatment Period.
- ^t Unless permitted in the protocol, all study activities, including assessments and sample collection, are expected to be completed on the same day (i.e., day of the visit).

5. PLANNED ANALYSES

The final analyses are based on final locked data and performed after all enrolled patients have completed the end of study visit. A separate database lock plan will describe details of the database lock.

6. GENERAL CONSIDERATIONS FOR DATA ANALYSES AND HANDLING

The efficacy and safety analyses use the analysis sets defined in Section 6.3. Patient listings (as appropriate) of all analysis data that support summary tables and/or figures are provided along with their source data. The summary tables do not include measurements from patients excluded from the pre-defined analysis sets or extra measurements (such as unscheduled or repeat assessments) not closest to the target study day unless specified otherwise, but the patient listings do include these data. Missing data are not imputed, unless otherwise specified. In general, patient listings are sorted by treatment group, patient number and assessment date (time and parameter, as applicable).

Any laboratory value (including eGFR), vital sign assessment, or ECG value collected after ESKD is considered invalid and will be treated as missing.

Efficacy and safety data collected while a patient has temporarily discontinued study drug will be included in analyses. All data will be presented in by-patient listings.

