### 9.1.9. End Stage Kidney Disease

Patients approaching end stage kidney disease (ESKD) should be closely monitored by the investigator to fully characterize their progression. For patients with eGFR  $\leq 15.0$  mL/min/1.73 m^2 (as calculated by the site, using the central lab-provided serum creatinine and the formulas provided in Section 9.10.18.1), initiate more frequent follow-up to closely monitor safety assessments (i.e., clinical chemistry (incl. eGFR), hematology, vital sign assessments (incl. weight), BNP and NT-proBNP). Similar frequent follow-up may also be implemented for patients with eGFR  $> 15.0$  mL/min/1.73 m^2 who, in the investigator's opinion based on the anticipated progression of their disease, may be approaching ESKD. Patient follow-up should be completed in-person or through a home health visit where in-person visits are not feasible, at least once every 4 weeks ( $\pm 2$  weeks), until one of the following occurs:

- Initiation of dialysis;
- Receipt of transplant.

Two off-treatment serum creatinine assessments should be collected 28 to 36 days after last dose, and prior to initiation of dialysis or receipt of transplant. Upon initiation of dialysis, study drug should be interrupted. Because laboratory and vital sign assessments can be affected by receiving dialysis, those safety assessments should not be performed concurrently while a patient is receiving dialysis. Patients receiving dialysis should continue to be followed for vital status and SAEs by phone or in-person according to the protocol scheduled visits. Dialysis not lasting at least 12 weeks will be considered acute dialysis, and patients should be considered for re-initiation of study drug with Medical Monitor approval. Such patients should continue to undergo frequent follow-up (i.e., at least once every 4 weeks ( $\pm 2$  weeks)) while eGFR  $\leq 15.0$  mL/min/1.73 m^2. Study drug may be re-started following acute dialysis, with Medical Monitor approval. Dialysis lasting at least 12 weeks will be confirmed as maintenance dialysis. Upon confirmation of maintenance dialysis, study drug should be discontinued.

Upon receipt of kidney transplant, study drug should be discontinued.

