6.6. Handling of Missing Data

6.6.1. Missing Efficacy Endpoint Data

Missing data will not be imputed for analyses of efficacy endpoints.

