8.4. Primary Endpoint

8.4.1. Primary Endpoint Analysis

The primary endpoint of this study is the off-treatment change from baseline in eGFR at Week 108. The ITT population will be used for all analyses. For all patients enrolled in the trial, Week 108 is the off-treatment eGFR assessed closest to 108 weeks after Study Day 1. For a patient who completed 2 years of treatment, the 8-week drug treatment withdrawal period occurs at Week 108 (i.e., 56 days after last dose). For a patient who stopped drug treatment early, the eGFR assessment at Week 108 is analyzed, irrespective of how long a patient has been off-treatment. Analysis of Week 108 (after a planned 8-week drug treatment withdrawal period) assesses the preserved drug benefit (relative to placebo) following withdrawal of treatment.

The off-treatment change from baseline eGFR at Week 108 for patients treated with bardoxolone methyl is compared to placebo using an ANCOVA model, with BASE_eGFR as a covariate, and TRT as fixed effects. The ANCOVA analysis uses eGFR values collected in the Week 108 analysis window (Section 6.5.2), which includes the follow-up assessment at Week 108 for patients who discontinued treatment early irrespective of time after last dose.

Missing Week 108 eGFR data will not be imputed.

The difference between bardoxolone methyl and placebo in change from baseline of eGFR is estimated along with the 95% confidence interval at Week 108.

Example SAS code as follows:

```
proc glm data=efficacy;
  class TRT ACR_STRAT;
  model DELT_eGFR=trt ACR_strat base_egfr /solution;
  lsmeans trt / diff stderr pdiff cl alpha=0.05;
run;
```

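### Patients who reach ESKD before the Week 108 window drop out of the primary ANCOVA, although it is labelled ITT

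*SAP*

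**What the plan says.** SAP Section 6 sets the rule for values after ESKD: "Any laboratory value (including eGFR), vital sign assessment, or ECG value collected after ESKD is considered invalid and will be treated as missing". The same section gives the default: "Missing data are not imputed, unless otherwise specified". Nothing visible in the efficacy sections specifies otherwise. Section 6.6.1 says "Missing data will not be imputed for analyses of efficacy endpoints", and Section 8.4.1 repeats it for the primary endpoint: "Missing Week 108 eGFR data will not be imputed".

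On which data enter the model, Section 8.4.1 says "The ANCOVA analysis uses eGFR values collected in the Week 108 analysis window". On the population it says "The ITT population will be used for all analyses", and Table 3 defines ITT as every enrolled patient in the arm to which they were randomized. Section 8.6.1.2 applies the same ANCOVA, again without imputation, at Week 112.

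Protocol Section 9.1.9 says that laboratory samples are not taken while a patient is on dialysis. After confirmed maintenance dialysis (at least 12 weeks) or transplant, follow-up is for vital status and SAEs only. The same section also says "Two off-treatment serum creatinine assessments should be collected 28 to 36 days after last dose, and prior to initiation of dialysis" (or transplant), and "Upon initiation of dialysis, study drug should be interrupted".

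**The concern.** Discarding a creatinine value that dialysis has altered is sensible. The difficulty is what happens next: the patient has no Week 108 value, no rule supplies one, and the model runs on those who remain. The patients removed are those whose kidneys failed, so the missingness depends directly on the outcome being measured, and adjusting for baseline eGFR does not repair that.

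At stake is the estimated difference in off-treatment eGFR change. If ESKD is more frequent in one arm, that arm loses more of its worst outcomes and looks better than it should. The ITT label tells the reader that all randomized patients are represented, which is not so here.

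**Working it through.** **1. The plan's own figure.** SAP Section 4.3.1 gives 850 patients randomized 1:1 (425 per arm), difference 2.3, SD 12 and two-sided alpha 0.05.
- Standard error = 12 × √(2/425) = 0.823. Then 2.3/0.823 = 2.794, 2.794 − 1.960 = 0.834, and Φ(0.834) = 0.798. This reproduces the stated power of about 80%.
- Solving for size gives 428 per arm (856), so 850 holds no allowance for missing Week 108 values. The same section assumes multiple imputation, which contradicts Sections 6.6.1 and 8.4.1.
- Losing 3% of patients lowers power only to 0.786. The issue is bias, not precision.

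**2. Tracing a patient.** ESKD occurs before the window; later eGFR is invalid (SAP 6); there is no imputation (SAP 6.6.1, 8.4.1); the ANCOVA reads only the window (Table 4: study days 756–783 for early stoppers, 56–83 days after last dose for completers). The patient contributes nothing. A Week 108 value taken before ESKD is still used.

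**3. Formula.** Let p be the ESKD share in an arm, m the mean change in patients without ESKD, and c the change assigned to ESKD patients. Then

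complete-case difference − all-patient difference = p_drug × (m_drug − c) − p_placebo × (m_placebo − c).

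This is for raw means; baseline adjustment in the ANCOVA would alter it somewhat.

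**4. Simple case (all assumed).** Baseline 33 for ESKD patients, and m = −6 in both arms. The shift is then (p_drug − p_placebo) × (−6 − c).

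| Assigned eGFR | c | −6 − c | 1-point imbalance | 2-point imbalance |
|---|---|---|---|---|
| 5 | −28 | 22 | 0.22 | 0.44 |
| 10 | −23 | 17 | 0.17 | 0.34 |
| 15 | −18 | 12 | 0.12 | 0.24 |

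The two-point column is 0.24/2.3 = 10% to 0.44/2.3 = 19% of the planned effect. Two points are 0.02 × 425 = 8.5 patients in one arm. More ESKD on drug overstates the benefit; more on placebo understates it. At equal rates the shift is zero.

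**5. Arm-specific means (also assumed).** m = −6.0 on placebo and −3.7 on drug, with c from −20 to −30.
- Equal ESKD of 1%, 2% or 3%: shift +0.02, +0.05 or +0.07.
- Drug 2%, placebo 1%: +0.19 to +0.29.
- Drug 3%, placebo 1%: 0.03 × 16.3 − 0.01 × 14 = +0.35, up to +0.55.
- Drug 1%, placebo 3%: −0.26 to −0.46.

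The order of magnitude agrees with step 4, but the ranges are no longer symmetric.

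**6. How common might ESKD be?** Entry needs a screening eGFR of at least 30. The protocol cites declines of 2.8 to 3.8 per year (Section 5) and 4.8 per year in its phase 2 ADPKD cohort (Section 5.1.1). From 33, two years at those rates leave 33 − 5.6 = 27.4 down to 33 − 9.6 = 23.4. ESKD by Week 108 therefore needs unusually fast decline.

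**The case against.** The strongest reply is that few patients will reach ESKD (step 6) and that no document supports an imbalance. The SAP's Introduction says that the diabetic kidney disease trial which led to the end of development showed no separation in end-stage events. Similar rates here would mean almost no bias. The SAP also presents all results as nominal and descriptive (Section 8.3). These points stand as limits on size and consequence. They do not remove the mechanism, and in a descriptive report the estimate and its interval are the result.

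Three stronger readings are tempting, and the documents do not support them.

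- A reader might infer that ESKD is hidden. It is not. Protocol 9.1.9 requires dialysis and transplant due to ESKD to be recorded as SAEs. SAP 9.1.2 tabulates serious treatment-emergent events by arm, and SAP 9.1 summarizes events more than 30 days after last dose separately. The Week 100 MMRM keeps values from before ESKD. Parts of SAP 8.6 are redacted, so a relevant sensitivity analysis there cannot be excluded. The tipping-point analysis promised in Protocol 12.3.1 does not appear in the visible SAP.
- A reader might infer from Protocol 9.1.9 that loss of the Week 108 value is near certain, because sampling 28 to 36 days off drug before dialysis cannot be combined with stopping drug at dialysis. The conflict exists only for patients dosed up to dialysis; drug may stop earlier for other reasons. Nor would resolving it restore a Week 108 value, since no visible rule carries those samples into the Table 4 window.
- A reader might infer that the rule favours the drug. The direction depends on which arm has more ESKD, and that is unknown.

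**Conclusion.** The point holds as a defect in the primary Week 108 ANCOVA and the Week 112 ANCOVA: patients are removed because of the outcome, under an ITT label. The resulting bias is near zero at equal ESKD rates. It is about 0.12 to 0.22 for a one-point imbalance and about 0.24 to 0.44 mL/min/1.73 m² for a two-point imbalance, in either direction. These figures rest on an assumed baseline of 33, a mean change of −6 in the other patients, an assigned eGFR of 5 to 15, and an imbalance that the documents neither state nor imply. The point merits a supplementary analysis; it does not show that the primary result is wrong.

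**What to change.** In SAP 8.4.1, add one pre-specified supplementary ANCOVA. Patients with ESKD before Week 108 stay in the model with an assigned eGFR of 5, 10 and 15 mL/min/1.73 m² in turn. Define ESKD by the events in Protocol 9.1.9: maintenance dialysis of at least 12 weeks, or transplant. The visible SAP only expands the abbreviation, so this also fixes the date from which values count as invalid.

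Restrict the analysis, in both arms, to patients whose scheduled Week 108 window fell on or before the end of study follow-up, and state the date used. Study drug was terminated on 10 May 2023. Without the restriction, every ESKD patient would be kept while event-free patients cut off before Week 108 stayed out, and ESKD would be over-represented. Varying the assigned value would not cure that.

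Report ESKD counts by arm beside the primary result. The events are already recorded as SAEs, so no new data are needed.

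The cost is one extra analysis, with an assigned value that is a convention; showing three values makes its influence visible. The analysis does not address Week 108 values missing for other reasons.

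Separately, for patients dosed up to dialysis, the two sentences in Protocol 9.1.9 on off-treatment sampling before dialysis and on interrupting drug at dialysis must be reconciled. This does not affect the Week 108 value.

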6.1. General Summary Table and Individual Subject Data Listing Considerations

Results of statistical analyses are reported using summary tables, listings, and figures (TLFs). All TLFs will use ICH numbering conventions. The strategy for controlling family-wise overall Type I error rate of 0.05 is described in Section 8.3. For endpoints not described in Section 8.4, the reported significance levels are nominal, and the following statistical conventions are used:

- Unless otherwise noted, all statistical testing is two-sided and is performed at the 0.05 significance level.
- Tests are declared statistically significant if the calculated p-value is <0.05 .

All analyses and summaries are produced using SAS[®] version 9.3 (or higher).

